# **3.** Antiplatelet agents following lower extremity endovascular intervention

It has been shown that dual antiplatelet therapy is a very important factor for short- and longterm success in coronary interventions. Thus, based on the results of randomized clinical trials,

current guidelines recommend dual antiplatelet therapy consisting of clopidogrel and aspirin for 12 months after percutaneous coronary intervention (PCI) for acute coronary syndromes and/or use of drug-eluting stents.

After peripheral artery interventions, there is still some uncertainty regarding the optimal periand post-interventional antiplatelet treatment of clopidogrel and/or aspirin

.6 The results of the Management of peripheral arterial interventions with mono or dual antiplatelet therapy (MIRROR) study showed that patients treated with clopidogrel+aspirin compared to aspirin alone had significantly lower target lesion revascularization (TLR) rates at 6 months. Nevertheless, the duration of dual antiplatelet therapy remains unknown and not been addressed by well-powered randomized clinical trials. The investigators of the MIRROR study therefore conducted an additional clinical follow-up of MIRROR patients at 12 months to evaluate the persistence or extinction of the clinical advantage of dual antiplatelet therapy. At 6 months, clopidogrel patients had significantly lower rates of TLR compared to placebo patients [2 (5%) vs. 8 (20%), p=0.04]. None of the TLR was due to thrombotic occlusion of previously recanalized arteries. There were no significant differences in the rate of binary restenosis at 6 months. After stopping clopidogrel/placebo, the significant difference in TLR disappeared [9 (25%) clopidogrel vs. 12 (32.4%) placebo (p=0.35)]. Thus in contrast to the first report of a reduction in the TLR at 6 months in the MIRROR study, this advantage of dual antiplatelet therapy does not persist after stopping clopidogrel. The investigators concluded that prolonged dual therapy (>6 months) should be considered in patients who are at high risk for restenosis.

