## 6. Trial endpoints

Clinical endpoints will be analyzed in all subjects who are enrolled, regardless of whether the trial treatment administered successfully completed for the desired duration. A subject will be considered enrolled in the trial when he/she is randomized to one of the treatment arms of the study. All endpoints are subject-based unless otherwise specified.

The primary endpoint is subject-based of the longer of a 12-month or end of study treatment endpoint of the first occurrence of index limb arterial occlusion, surgical intervention,

endovascular intervention, amputation of the affected limb (primary patency and limb salvage), MI, ischemic stroke or death (survival)

The secondary endpoints are subject-based on the longer of a 12-month or end of study treatment endpoints that include: (a) the first occurrence of any individual component of the primary endpoint, (b) the first occurrence of the following during follow-up: cardiovascular death, or MI, or ischemic stroke, or any amputation above the ankle and (c) severe bleeding defined according to the Global Utilization of Streptokinase and Tissue plasminogen activator for Occluded coronary arteries (GUSTO) classification

The tertiary endpoint is based on the longer of a12-month or end of study treatment moderate bleeding according to the GUSTO classification

Clinically indicated DAPT duration will be based on the longest pre-discharge following index peripheral intervention procedure DAPT duration. This will be determined based on: peripheral intervention device IFUs, preceding coronary intervention, acute coronary syndrome or other guideline-based clinical or device specific DAPT duration.

Study treatment will be discontinued at the first occurrence of a primary endpoint as defined in the table below. Patients, however, can resume taking aspirin, Clopidogrel, or both based on their provider's clinical decision.

Primary endpoint definition(s)	Secondary/Tertiary endpoint definition(s)
Occlusion of the target limb documented by any imaging procedure performed clinically	As described in section 6, except for:
any maging procedure performed ennearly	GUSTO bleeding criteria:
Any surgical or endovascular	1. Severe or Life-threatening: Intracerebral hemorrhage resulting in substantial
revascularization procedure on the index limb	hemodynamic compromise requiring treatment
Amputation above the ankle of the index	2. Moderate: Requiring blood transfusion but not resulting in hemodynamic

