## **12. Trial procedures**

The schedule of observations and assessments to take place during the trial are listed in **Table 2.** 

Table 2: Trial Event Schedule

	enrollment	30day (±7days)	6m  (± 15 days)	12m and q6m till end of study treatment  (±15 days)
Informed consent	+			
Inclusion/Exclusion	+			
Physical Examination 	+	+	+	+
Rutherford Classification	+	+	+	+
ABI	+	+	+	+
TASC classification	+			
Serum creatinine	+	+	+	+
Hemoglobin	+	+	+	+
Platelet count	+	+	+	+
Recommended Anti- Coagulant Therapy Assessment	+	+	+	+
WIQ (section 1)	+	+	+	+
AE assessment 		+	+	+
Concomitant medications	+	+	+	+

1. Physical examination includes gross assessment of standard organ systems (e.g., cardiac, pulmonary, etc).

2. AE assessments and reporting include AE, SAE and MAE.

- 3. End of study treatment visit will be performed when patient completes duration of assigned study treatment. This visit may fall between q6m visit schedule for some patients.
- 4. Phone visits can be done if patients refuse in-clinic visit during the follow up period, or who are do not show up to their follow up visits. Labs and ABIs will be collected and

documented, if available in their medical records during the follow up period. Study team should document 2 attempts to schedule in-clnic visits before phone visits are completed during follow-up

5. Patients who do not complete their follow up visits in -clinic will not be provided a refill of aspirin and Plavix (if randomized to the long arm) They will remain on the study as ITT and phone follow-up may be completed to collect data. Prescriptions may be renewed when patients complete an in-clinic visit.

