## 18. Availability of aspirin and clopidogrel

As both these drugs are approved worldwide and used routinely in post endovascular interventions, they would be used on the basis of use as per routine clinical practice and as per local/regional drug procurement and dispensing practices.

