#### **Risk minimization**

The risks associated with the aspirin and clopidogrel use are relatively well established, and the preceding risks represent the most up-to-date understanding of risks associated. The study team will employ measures throughout the course of this investigation, to minimize these risks to subjects choosing to participate. In general, efforts will be made to minimize these risks by:

- i. Selecting Investigators who are experienced and skilled clinicians and expert in endovascular procedures
- ii. Clearly defining inclusion/exclusion criteria to ensure only appropriate subjects are enrolled
- iii. Ensuring that the treatment and follow-up of the subjects are consistent with current medical practices

Specifically, every subject participating in this trial will undergo the following:

- a. Medical history, physical examination, and laboratory assessment prior to the procedure to identify factors which may increase risk
- b. Required review of anti-coagulant and anti-platelet medication before and after enrolment into the trial

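### Table 2 note 5 refuses trial refills after a 6-month or later visit not done in clinic, with no exception for the clinically indicated period, and so conflicts with the assigned regimen for a long-arm subject whose indication is still running

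*Combined protocol and SAP*

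**What the plan says.** Section 12, Table 2, attaches notes 4 and 5 to the 6-month column and to the column for month 12 and later, but not to the 30-day column. Note 4 allows a phone visit when a patient refuses or does not attend: "Study team should document 2 attempts to schedule" an in-clinic visit before the phone visit is done. Note 5 says that patients who do not complete these visits in clinic "will not be provided a refill of aspirin and Plavix (if randomized to the long arm"). They stay in the intention-to-treat set and may be followed by phone. The only stated way back to a refill is this: "Prescriptions may be renewed when patients complete an in-clinic visit".

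Section 9 assigns aspirin plus clopidogrel for the clinically indicated duration, with a 30-day minimum, in the control arm, and for the indicated duration plus 12 months in the treatment arm. Section 6 takes the longest applicable duration, based on peripheral device instructions or "preceding coronary intervention, acute coronary syndrome or other guideline-based clinical or device specific DAPT duration", and sets no maximum. Section 3 reports that the guidelines in force call for "dual antiplatelet therapy consisting of clopidogrel and aspirin for 12 months after percutaneous coronary intervention (PCI) for acute coronary syndromes". It names drug-eluting stents as a further basis for the same duration.

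Section 18 says of the two drugs that "they would be used on the basis of use as per routine clinical practice and as per local/regional drug procurement and dispensing practices".

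**The concern.** Treatment in the long arm has two phases. The first is indicated therapy, which the subject would need outside the trial and which controls are assigned as well. The second is the additional 12 months, which is the experimental part. Making a trial refill depend on a clinic visit is unremarkable in the second phase. Note 5 does not separate the phases, so as written it also reaches the first.

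What is at stake is a possible gap in dual therapy while a recent coronary indication is still running, in a trial whose primary endpoint includes MI and death. This is a patient-safety matter, not one of power or type I error.

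The parenthesis in note 5 is also unclear. It may cover Plavix alone or both drugs. It may limit the refusal to the long arm, or it may only identify who receives trial clopidogrel. On none of these readings is a clopidogrel restriction stated for controls, although they are on the same therapy during the indicated period.

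**Working it through.** The plan gives no figure on this point, so there is none to reproduce, and the sample size does not bear on it. The check sets the provisions side by side and adds one timing condition.

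1. **When the rule applies.** Note 5 applies from the 6-month visit onward. An indication that has ended by then, including one at the 30-day minimum, is unaffected.
2. **Whether visits outside the clinic are expected.** They are. Note 4 provides for them.
3. **Whether the indicated period is part of long-arm study treatment.** It is. Section 9 assigns the indicated duration plus 12 months.
4. **Whether the indication can still be running at that visit.** Assume that the 12 months in Section 3 run from the coronary event and that visits are counted from the index procedure. Let k be the months from the coronary event to the index procedure. The indication remaining at the index procedure is 12 − k months. It outlasts a visit at month 6 when 12 − k > 6, that is, when k < 6. The ±15-day window puts that visit between about 5.5 and 6.5 months, so the bound on k lies between 12 − 6.5 = 5.5 and 12 − 5.5 = 6.5 months. A subject whose coronary event was more recent than that is still in the indicated period. The exclusion criteria in Section 10 rule out planned cardiac procedures, not preceding ones.
5. **What the two provisions then require.** For a long-arm subject in step 4 who is seen by phone, Section 9 assigns clopidogrel and note 5 denies the trial refill until a clinic visit.
6. **Whether another provision resolves the conflict.** Section 18 makes routine supply possible but directs no one to arrange it. Section 24 has a general commitment: "Ensuring that the treatment and follow-up of the subjects are consistent with current medical practices". It does not say which provision gives way. Section 6 does address resumption after a primary endpoint, where "Patients, however, can resume taking aspirin, Clopidogrel, or both" on their provider's decision. Note 5 has no matching clause.

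**What cannot be computed.** The documents do not give the share of subjects with such an indication, the rate of visits outside the clinic, the refill quantity, or how long subjects would take to return. Neither the number affected nor the time lost can be estimated.

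**The case against.** The strongest reply is that refusing a trial refill is not stopping the drug. Note 5 tells no one to discontinue therapy and does not bar a treating clinician from prescribing. Both drugs are in routine use, and with routine-care supply nothing is lost. Such a prescription would breach nothing in note 5 and would follow the Section 9 assignment, so the adherence rules in Section 25 do not stand in its way. Section 24 requires review of antiplatelet medication before and after enrolment, and Table 2 lists concomitant medications at every visit, so a gap could be noticed. The rule also has a sound purpose: the clinic visit provides haemoglobin, platelet count, creatinine and an examination for patients on dual therapy.

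Most of this stands, and it limits the point to a possible interruption. It does not remove the conflict. Routine supply is allowed, not required. The medication review names no remedy. The plan sets no laboratory threshold that a subject must meet to get a refill, and no such condition is stated for controls on the same indicated therapy.

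Three stronger readings are tempting, and the documents do not support them:

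- A reader might infer that sites have no instruction to continue indicated therapy. Section 9 gives that instruction for both arms. The fault is that note 5 conflicts with it.
- A reader might infer that note 5 will stop indicated treatment. That also needs the trial supply to run out and no other source of the drug.
- A reader might want to state the share of subjects affected or of indicated months lost. Any such figure would rest on inputs that the documents do not give.

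**Conclusion.** The point holds as a minor one. Note 5 states a rule without exception, and for a long-arm subject still in the indicated period at a 6-month or later visit that rule conflicts with the regimen assigned in Section 9. Indicated clopidogrel could be interrupted unless routine care supplies it.

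The conclusion rests on reading note 5 as written and on the Section 3 guideline duration as an example of an indication longer than 6 months. Section 3 is background, not a protocol duration rule, but Section 6 brings guideline-based durations into the assigned regimen. Exposure requires four things together: assignment to the long arm, an indication still running, a visit not done in clinic, and no other supply. Frequency is unknown.

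**What to change.** Add to note 5: *The in-clinic condition on refills applies only to the additional 12 months. Until the clinically indicated duration under Section 6 ends, aspirin and clopidogrel are continued in both arms, by trial refill or by a confirmed routine-care prescription, whether or not the visit took place in clinic.*

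Also state whether the parenthesis covers Plavix alone or both drugs. Simply deleting it would be a mistake, because that could extend the refusal to controls.

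The cost is a short footnote amendment with IRB approval and no new data collection. A routine-care prescription can be confirmed in the concomitant-medication review already scheduled at each visit. There are two downsides. Sites lose a little leverage for clinic attendance during the indicated period, and some refills would be given without a trial check of haemoglobin, platelets and creatinine, although note 4 already takes laboratory results from the medical record where available. The in-clinic condition stays in force for the additional 12 months.

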## **13. Informed consent**

All subjects who are potential trial candidates must provide written informed consent before enrollment.

Subjects must sign the trial-specific, most recent version of the Institutional Review Board (IRB) approved Informed Consent form before any trial-specific interventions. Trial personnel should explain to the subject that even if a he or she agrees to participate in the trial and signs an Informed Consent form, careful assessment of inclusion/exclusion criteria may demonstrate that the subject is not a suitable candidate for the trial, and, therefore, the subject will not be allowed to participate.

Trial Center personnel will maintain a Screening/Enrollment Log to document enrolled subjects and select information about candidates who fail to meet the general or angiographic entry criteria.

## 14. Sample size estimate

The occurrence of the primary endpoint is expected to be approximately 49% in the control group, derived on the basis of current literature review and preliminary data form XLPAD registry.

A 30% relative risk reduction in the incidence of primary endpoint would be clinically important. To detect a 30% relative reduction in the primary event rate from 49% to34%  with 80% power at the two-sided, 0.05 significance level, assuming a 12-month recruitment period and a 10% dropout rate at 1 year, a total of 404 patients will be randomized (202in each group) and followed-up for endpoints for longer of a 12-month or end of study treatment period.

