	agents (history of intra-cerebral bleed, presence of intracerebral
	mass, recent or <6 weeks gastrointestinal bleed, blood
	transfusion within the last 6 weeks, any trauma requiring surgery
	or blood transfusion within the last 4 weeks or any surgical
	procedure within the last 4 weeks.
	Angiographic:
	• Endovascular intervention to iliac, FB or BTK
	artery bypass graft
	Persistent, intraluminal thrombus of the
	proposed target lesion at the completion of
	the index procedure
	• Perforated vessel as evidenced by extravasation of contrast media
	
 
Vascular graft, aneurysm or postsurgical stenosis of the target vessel
 

Multiple Interventions	Multiple interventions during an index procedure will be allowed as
During Index Procedure	long as the procedure is deemed successful and uncomplicated by the
	primary operator and no additional procedures are planned
Statistical Methods	
Sample size parameters	• The occurrence of the primary endpoint is expected
Sampre Size parameters	to be approximately 49% at 12 months in the
	control group 
	
 
A 30% relative risk reduction in the incidence of primary
 

	endpoint would be clinically important
	
 
To detect a 30% relative reduction in the 1-year primary
 

	event rate from $49\%$ to $34.0\%^{17}$ with $80\%$ power at the two sided 05 significance level assuming a 12 month
	two-sided, .05 significance level, assuming a 12-month
	two-sided, .05 significance level, assuming a 12-month recruitment period and a 1 0 % dropout rate at 1 year, a total
	two-sided, .05 significance level, assuming a 12-month recruitment period and a 1 0 % dropout rate at 1 year, a total of 404 (368+36) patients will be randomized (202 in each
	two-sided, .05 significance level, assuming a 12-month recruitment period and a 1 0 % dropout rate at 1 year, a total of 404 (368+36) patients will be randomized (202 in each group) and followed-up for endpoints for 12 months or until
	two-sided, .05 significance level, assuming a 12-month recruitment period and a 1 0 % dropout rate at 1 year, a total of 404 (368+36) patients will be randomized (202 in each
Statistical analysis	two-sided, .05 significance level, assuming a 12-month recruitment period and a 1 0 % dropout rate at 1 year, a total of 404 (368+36) patients will be randomized (202 in each group) and followed-up for endpoints for 12 months or until end of study treatment, whichever is longer

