Peripheral catheter interventions are performed under local anesthesia allowing early and full mobilization. However, as a result of this intervention, atherosclerotic plaques are ruptured and platelets aggregate at the site of injury. Extensive vessel wall damage coupled with low shear stress and poor infrapopliteal outflow are mostly responsible for the occurrence of reocclusion.

Additionally, in the initial phase after catheter intervention, a hypercoagulable state prevails, as parameters of activated coagulation, including thrombin-antithrombin complexes (TAT), D-Dimer and Fibrinopeptide A (Fa) become elevated in the plasma. This activated coagulation system produces conditions favorable for early thrombotic occlusion, where 'early' is usually defined as a period covering the first four weeks after the intervention. Subsequently, intimal hyperplasia may follow which is responsible for intermediate and late-term restenosis and reocclusion. Intimal hyperplasia occurs as a result of denudation (tearing off of the inner lining) of the endothelium caused by manipulation of the vessel wall with the catheter. Reported rates of arterial reocclusion or symptomatic restenosis following femoropopliteal PTA are between five and twenty-five per cent for early events and about 40% one year. The five year patency rate was reported to be 83% for iliac and 58% for femoropopliteal PTA, whilst patients with stenoses or occlusions of less than 3 cm had a favorable long-term patency rate of 74%

Patients with CLI or those subjected to local thrombolysis show higher incidences of reocclusion. The implantation of drug-eluting or nitinol stents, or treatment by intravascular brachytherapy following PTA are considered as interventions with the capacity of reducing the occurrence of intimal hyperplasia, however may be associated with delayed endothelialization

and increased risk of thrombosis.

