## 9. Method of assigning subjects to treatment

Patients scheduled for a planned discharge will be randomized on a 1: 1 basis using a central computerized randomization portal available through RedCap® to either of the following treatment groups:

ASA (81 mg/d for U.S. sites; 75-100 mg for international sites) + clopidogrel:for clinically indicated duration with a minimum of 30 days (control arm)

ASA (81 mg/d for U.S. sites; 75-100 mg for international sites) + clopidogrel 75 mg: for clinically indicated duration + 12m (treatment arm)

An inclusion and exclusion checklist needs to be completed via computerized randomization portal available through  $RedCap^{(R)}$  prior to randomization of the subject.

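### The sample size uses a 1-year drop from 49% to 34% but makes no allowance for the initial period when both arms take the same drugs, so that net effect is not justified

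*Combined protocol and SAP*

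**What the plan says.** **Planned effect.** Section 14 states: "The occurrence of the primary endpoint is expected to be approximately 49% in the control group". It then sizes the trial as follows: "To detect a 30% relative reduction in the primary event rate from 49% to34" percent, "with 80% power at the two-sided, 0.05 significance level", with "a 10% dropout rate at 1 year". The Synopsis (Sample size parameters) ties the effect to one year: "To detect a 30% relative reduction in the 1-year primary" event rate. The total is 404 randomised, 202 per arm. Section 20 (Primary Endpoint) expects at least 184 evaluable per arm.

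**Treatment.** Section 9 gives the control arm aspirin plus clopidogrel "for clinically indicated duration with a minimum of 30 days (control arm"). The test arm takes the same drugs for the indicated duration and then for 12 more months. Under Section 6, the indicated duration is set patient by patient from device instructions, earlier coronary intervention, acute coronary syndrome or guidelines. No upper limit or expected distribution is given. The Synopsis has randomisation within 2 weeks of the procedure.

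**Analysis.** Section 17 makes intention-to-treat primary. The Synopsis, Section 6 and Section 14 run the endpoint to the later of 12 months or end of study treatment. Section 20 analyses a 12-month composite.

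**The concern.** Assigned treatment cannot separate the arms while both are taking the same drugs. Randomisation comes at the start of that period, so events within it enter both arms alike and dilute the contrast. Section 3 itself suggests that benefit depends on continued exposure: in the cited trial of dual versus single antiplatelet therapy, the advantage in target lesion revascularization was lost once clopidogrel stopped. The sample size text nevertheless has no lag, no dilution and no expected mix of durations.

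Section 8 presents the trial as the one to settle the duration question, after earlier studies that were underpowered or abandoned. If power is materially below 80%, a null result could not separate lack of benefit from too short a period of differing treatment.

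**Working it through.** **Step 1. Reproduce 404.** Inputs from Section 14: 49% versus 34%, two-sided 0.05, 80% power, 10% dropout. The difference is 0.15 and the mean rate 0.415.

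- Without continuity correction: n = [1.960 × √(2 × 0.415 × 0.585) + 0.842 × √(0.49 × 0.51 + 0.34 × 0.66)]² / 0.15² = 168.2, so 169 per arm.
- With continuity correction: (168.2 / 4) × [1 + √(1 + 4 / (168.2 × 0.15))]² = 181.3, so 182 per arm, 364 in total.
- With dropout: 364 / 0.9 = 404.4, so 405 against the stated 404.

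The plan's figure is therefore a plain comparison of two 12-month proportions. It contains no shared period.

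**Step 2. Express the planned effect as a hazard ratio.** This is a modelling assumption; the plan gives only cumulative rates. With constant hazard, control λ = −ln(0.51) = 0.673 per year, and HR = ln(0.66) / ln(0.51) = 0.617.

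**Step 3. Let the effect start at divergence, d months in.**

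- Horizon A, 12 months in both arms: control 49%; test = 1 − exp[−λ(d + 0.617(12 − d)) / 12].
- Horizon B, d + 12 months in both arms: control = 1 − exp[−λ(d + 12) / 12]; test = 1 − exp[−λ(d + 0.617 × 12) / 12].

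Power is for two proportions at 184 per arm, without continuity correction. Only d = 1 comes from the documents (the 30-day minimum); the longer values are assumptions.

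| d (months) | Test rate, A | Power, A | Rates, B | Power, B |
|---|---|---|---|---|
| 0 | 34.0% | 83% | 49.0% vs 34.0% | 83% |
| 1 | 35.4% | 75% | 51.8% vs 37.6% | 78% |
| 3 | 38.1% | 56% | 56.9% vs 44.2% | 68% |
| 6 | 42.0% | 27% | 63.6% vs 52.9% | 55% |
| 12 | 49.0% | no contrast | 74.0% vs 66.3% | 36% |

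With continuity correction, horizon A gives 81%, 72%, 52% and 24% at 0, 1, 3 and 6 months.

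**Step 4. Post-divergence effect needed for 34% at 12 months.** Required HR = [−ln(0.66) − λd/12] / [λ(12 − d)/12]. This is 0.58 at 1 month, 0.49 at 3 and 0.23 at 6.

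**Step 5. Power of a landmark analysis.** Take 202 × 0.90 = 181.8, so 181 per arm, and keep those event-free at d: 181 × exp(−λd/12) = 171, 153 and 129 at 1, 3 and 6 months.

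- Followed for 12 months after the landmark (49% vs 34%): 81%, 76% and 69%.
- If control data stop at month 12, the window is 12 − d months. The rates are 46.1% vs 31.7%, 39.7% vs 26.8% and 28.6% vs 18.8%, and power is 78%, 67% and 46%.

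**The case against.** **The plan's power is correct for what it states.** This stands. Section 14 gives cumulative rates and calls a 30% reduction clinically important. It never says the effect acts from day 0, and 0.617 is a derived figure. A reader might infer that the 80% is miscalculated; the documents do not support that. What is missing is a reason to expect a net 34% given the overlap.

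**The endpoint is not simply 12 months.** This also stands in part. Most sections use the later of 12 months or end of study treatment, so the horizon A figures alone would overstate the loss. Horizon B softens the loss without restoring 80%. It also assumes controls are followed as long as test subjects, which the plan does not clearly provide.

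**Most subjects may have only 30 days.** Possible, and the loss is then about 8 points. If the 30 days run from the procedure and randomisation comes on day 14, the shared time after randomisation is about 16 days and the loss smaller still. The plan gives no distribution either way.

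**Two stronger readings should be resisted.** Section 3 says "current guidelines recommend dual antiplatelet therapy consisting of clopidogrel and aspirin for 12 months after percutaneous coronary intervention", from which a reader might infer that many subjects have no first-year contrast at all. That statement concerns acute coronary syndromes and/or drug-eluting stents, and part of the period may already have elapsed at the index procedure. Section 3 also reports reocclusion or symptomatic restenosis "between five and twenty-five per cent for early events and about 40% one year", and a reader might subtract the early share from the 49%. Those rates are for femoropopliteal angioplasty and a different outcome. This trial also enrols iliac and below-the-knee cases, excludes complicated procedures and persistent thrombus, and randomises up to 14 days later. The subtraction is not valid here.

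**Conclusion.** The point holds as a gap in justification; the sample size arithmetic is sound. If the planned effect operates only once treatment differs, 12-month power is about 75% at the documented 30-day minimum, against 83% with no overlap on the same method. Larger losses (56% at 3 months, 27% at 6) depend on durations the documents do not give, and they shrink to 68% and 55% if both arms are followed to overlap plus 12 months. All figures assume constant hazard, HR 0.617 after divergence, a common overlap for all subjects and 184 per arm. A stronger post-divergence effect could still yield 34%, but the plan does not argue for one. The matter should be corrected before the analysis is fixed; it does not invalidate the design.

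**What to change.** 1. **Section 14 and Synopsis.** Restate power with the shared period included. Lead with the 30-day case and show longer overlaps under both horizons. Alternatively, state that 30% is the net effect and give the post-divergence hazard ratio it implies.
2. **Endpoint horizon.** Reconcile the 12-month composite in Section 20 with the later-of rule in Sections 6 and 14, so that both arms share one horizon. Taken literally, the later-of rule can follow test subjects longer than controls, which biases a comparison of proportions against the test arm.
3. **Supportive landmark analysis.** Record each subject's indicated duration before randomisation. Start the analysis at the end of that duration, among subjects event-free and still in follow-up, over a window covered in both arms. Keep intention-to-treat as primary.

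**Cost.** Items 1 and 2 are mainly wording, and the stated power becomes less favourable. A common horizon beyond month 12 may need extra control visits. The landmark analysis drops early events. It also assumes no arm-related dropout before the landmark, in a trial that appears open-label: no blinding of subjects is described, and the Table 2 refill note refers to the long arm. Its power is 78%, 67% and 46% at 1, 3 and 6 months of overlap if control data stop at month 12. The 81%, 76% and 69% figures apply only if controls are followed to overlap plus 12 months.
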